### **1.1. Experience with the use of convalescent plasma against coronavirus diseases**

In the 21st century, there were two other epidemics with coronaviruses that were associated with high mortality, SARS1 in 2003 and MERS in 2012. In both outbreaks, the high mortality and absence of effective therapies led to the use of convalescent plasma. The largest study involved the treatment of 80 patients in Hong Kong with SARS (Cheng et al., 2005). Patients treated before day 14 had improved prognosis defined by discharge from hospital before day 22, consistent with the notion that earlier administration is more likely to be effective. In addition, those who were PCR positive and seronegative for coronavirus at the time of therapy had improved prognosis. There is also some anecdotal information on the use of convalescent plasma in seriously ill individuals. Three patients with SARS in Taiwan were treated with 500 ml of convalescent plasma, resulting in a reduction in plasma virus titer and each survived (Yeh et al., 2005). Three patients with MERS in South Korea were treated with convalescent plasma, but only two of the recipients had neutralizing antibody in their plasma (Ko et al., 2018). The latter study highlights a challenge in using convalescent plasma, namely, that some who recover from viral disease may not have high titers of neutralizing antibody (Arabi et al., 2016). Consistent with this point, an analysis of 99 samples of convalescent sera from patients with MERS showed that 87 had neutralizing antibody with a geometric mean titer of 1:61. This suggests that antibody declines with time and/or that few patients make high titer responses.

It is also possible that other types of non-neutralizing antibodies are made that contribute to protection and recovery as described for other viral diseases (Gunn et al., 2018; van Erp, Luytjes, Ferwerda, & van Kasteren, 2019). There are reports that convalescent plasma was used for therapy of patients with COVID-19 in China during the current outbreak (Xinhua, 2020). Although few details are available from the Chinese experience and published studies involved small numbers of patients, the available information suggests that convalescent plasma administration reduces viral load and was safe.

Convalescent plasma, compared to normal control plasma, was recently shown to confer lower mortality in New York City and Brazil among adults hospitalized with

severe COVID-19; overall clinical status based on an ordinal scale at Day 28, however, did not differ between the two arms (O'Donnell, 2021)

## 1.2. Overview of known potential risks

Historical and current anecdotal data on use of convalescent plasma suggest it is safe in coronavirus infection. Therefore, the large number of exposed healthcare workers, public servants and first responders, in combination with the high mortality of COVID-19, particularly in elderly and vulnerable persons, strongly argue that the benefits of convalescent serum outweigh its possible risks in high risk exposed individuals and/or those with early disease. However, for all cases where convalescent plasma administration is considered, a risk-benefit assessment must be conducted to assess individual variables.

The theoretical risk involves the phenomenon of antibody-mediated enhancement of infection (ADE). ADE can occur for several viral diseases and involves an enhancement of disease in the presence of certain antibodies. For coronaviruses, several mechanisms for ADE have been described and there is the theoretical concern that antibodies to one type of coronavirus could enhance infection to another viral strain (Wan et al., 2020). It may be possible to predict the risk of ADE of SARS-CoV-2 experimentally, as proposed for MERS. Since the proposed use of convalescent plasma in the COVID-19 epidemic would rely on preparations with high titers of neutralizing antibody against the same virus, SARS-CoV-2, ADE may be unlikely. The available evidence from the use of convalescent plasma in patients with SARS1 and MERS (Mair-Jenkins et al., 2015), and anecdotal evidence of its use in patients with COVID-19 (Xinhua, 2020), suggest it is safe. Nevertheless, caution and vigilance will be required in for any evidence of enhanced infection.

Another theoretical risk is that antibody administration to those exposed to SARS-CoV-2 may avoid disease but modify the immune response such that those individuals mount attenuated immune responses, which would leave them vulnerable to subsequent re-infection. In this regard, passive antibody administration before vaccination with respiratory syncytial virus was reported to attenuate humoral but not cellular immunity (Crowe, Firestone, & Murphy, 2001). This concern will be investigated as part of this clinical trial by measuring immune responses in those exposed and treated with convalescent plasma to prevent disease. If the concern proved real these individuals could be vaccinated against COVID-19 when a vaccine becomes available.

Passive antibodies are derived from human serum. The antibodies used in this study will be derived from serum obtained from convalescent patients and will be subjected to testing protocols that are similar to those used by blood banks and transfusion services. However, as is the case with any biological product, there is a very small risk of allergy/anaphylaxis, transfusion related acute lung injury (TRALI), and transfusion associated circulatory overload (TACO) or passive transfer of potential unknown infectious agents or infections. Most adverse effects are mild and

transient including headaches, flushing, fever, chills, fatigue, nausea, diarrhea, blood pressure changes and tachycardia. Late adverse events are rare and include acute renal failure and thromboembolic events.

### **1.3. Known potential benefits**

A benefit of convalescent plasma administration is that it can prevent infection and subsequent disease in those who are at high risk for disease following close contacts of patients with COVID-19. This is especially so for those with underlying medical conditions. Many who will qualify for prophylaxis are health care workers and first responders who are critical to maintenance of stability of the healthcare system. Passive antibody administration to prevent disease is already used in clinical practice. For example, patients exposed to hepatitis B and rabies viruses are treated with hepatitis B immune globulin (HBIG) and human rabies immune globulin (RIG), respectively. Botulism Immune Globulin Intravenous (Human) (BIG-IV) is an intravenous preparation for infant botulism. In addition, passive antibody is used for the prevention of severe respiratory syncytial virus (RSV) disease in high-risk infants. Until recently, polyclonal hyperimmune globulin (RSV-IG) prepared from donors selected for having high plasma titers of RSV neutralizing antibody, was used but these preparations have now been replaced by palivizumab, a humanized murine monoclonal antibody.

Another potential benefit is societal: If the frequency with which exposed persons become infected decreases, the risk of further transmission ( $R_{naught}$ ) might be reduced and the epidemic slowed. Another avenue (not pursued in this protocol) is as a treatment for established infection. Convalescent plasma would be administered to those with clinical disease in an effort to reduce their symptoms and mortality. Based on the historical experience with antibody administration, it can be anticipated that antibody administration would be more effective in preventing disease than in the treatment of established disease.

Given that historical and current anecdotal data on use of convalescent plasma suggest it is safe in coronavirus infection, the high mortality of COVID-19, particularly in elderly and vulnerable persons, suggests that the benefits of its use in those at high risk for or with early disease outweigh the risks. However, for all cases where convalescent plasma administration is considered, a risk-benefit assessment must be conducted to assess individual variables.

### **1.4. Albumin (Human) 5% as Control Study Product**

Participants randomized to the control arm will receive albumin (human) 5% infusion. The albumin will be prepared in bags that are as similar as possible to the bags used for plasma. The similar appearance of albumin and plasma will facilitate maintaining the blinded status of subjects and most of the study staff. Saline

solution or standard of care (no intervention at all) would not allow the subjects to remain blinded and if not blinded, subjects who receive convalescent plasma may alter their behavior, resulting in additional exposure to SARS-CoV-2 and risk of COVID-19.

While normal plasma is only very rarely associated with adverse reactions such as febrile, allergic, anaphylactic and hemolytic events, the risks of albumin infusions are even less frequent. Albumin infusions are rarely associated with rigors, hypotension/decreased BP, tachycardia/increased heart rate, pyrexia, feeling cold (chills), nausea, vomiting, dyspnea/bronchospasm, rash/pruritus as per the package insert. The risk of an anaphylactoid reaction to albumin is not described in the package insert but was observed with only 0.01% of over 60,000 units of infused albumin [Gales BJ and Erstadt BL, 1993]. Since then, the purification methods for albumin have improved even further. There is no risk of an ABO mismatch with albumin. The main risk of albumin infusion, as with plasma, is related to the risk of rapid volume expansion. The risk of volume overload will be mitigated by transfusing study product (CP plasma or albumin) over a 1- to 4-hour period, at the clinician's discretion, depending on the subject's medical history and clinical status.

## **1.5. SARS-CoV-2 testing**

The Laboratorio de Pesquisa em DST e AIDS do IPEC/FIOCRUZ (LAPCLIN/AIDS), Laboratório de Virus Respiratórios e Sarampo (IOC/FIOCRUZ) or the Center for Infection and Immunity (CII) laboratory will conduct both a quantitative PCR assay and serologic assay. No clinical decisions will be made based on these results.

For asymptomatic individuals, PCR testing alone will be used for screening. For symptomatic individuals, two swabs will be collected from each potential participant, one for ID NOW (or comparable rapid antigen test) and one for a PCR-based test. The ID NOW test results are available in minutes and will make recruitment more efficient. In view of the high specificity of the ID NOW test (99.7%) (Dinnes, et al., 2021), if either the ID NOW and/or the PCR test results is positive, the individual will be confirmed as SARS-CoV-2 positive.

PCR testing will be conducted for all participants at screening, days 0, 3, 7, 14 and 28 and the viral load will be estimated. Results from the baseline ID NOW COVID-19 or PCR tests will be reported to subjects as SARS-CoV-2 positive or negative. Subsequent PCR results will not be shared with the subjects or the clinical research team in order to reduce bias.

ID NOW COVID-19 assay performed on the ID NOW Instrument is a rapid molecular in vitro diagnostic test utilizing an isothermal nucleic acid amplification technology intended for the qualitative detection of nucleic acid from the SARS-CoV-2 viral RNA in direct nasal, nasopharyngeal or throat swabs from individuals who are suspected

of COVID-19 by their healthcare provider within the first seven days of the onset of symptoms. ID NOW COVID-19 received Emergency Use Authorization from the US FDA in September 2020.

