## 2.3 Study population

### 2.3.1 Inclusion Criteria for Enrollment

1. Subjects must be 18 years of age or older
2. a. Recent close contact3\* with a person with COVID-19, i.e. last close contact occurred within 7 days of anticipated infusion of study product. It is anticipated that most contacts will be household contacts with extensive interaction. All must meet the CDC criteria for close contacts. This includes healthcare workers at higher risk of developing severe disease.  
OR  
b. Recent self-reported or documented evidence of infection by nasal swab ID NOW or PCR that is positive for SARS-CoV-2, i.e., nasal sample was collected within 7 days or 10 days of anticipated infusion of study product for those who are asymptomatic or symptomatic, respectively.
3. Evidence of infection by nasal swab ID NOW or PCR that is positive for SARS-CoV-2 at screening visit

---

 Close contact is defined by CDC as being within approximately 6 feet (2 meters) of a COVID-19 case for a prolonged period of time (without PPE); close contact can occur while caring for, living with, visiting, or sharing a healthcare waiting area or room with a COVID-19 case.

 7 days (if asymptomatic at prescreening) or 10 days (if minimally to moderately symptomatic during prescreening) are based on the number of days from specimen collection date to anticipated infusion date

 A repeat ID NOW and PCR at screening is required for all participants. However, for participants with documented evidence of infection by nasal swab PCR that is positive for SARS-CoV-2 in the prior week, a positive swab is not required to enroll the participant since they were already positive in the past week and will be tested by PCR during the Infusion Visit. At screening, two swabs will be collected from each participant, one for ID NOW (or comparable rapid antigen test) and one for a PCR-based test. If ID NOW is positive, it will not be necessary to wait for the PCR based test result to confirm the positive. If the ID NOW is negative, it will be necessary to wait for the PCR test result: PCR negative will mean individual is not eligible and PCR positive will mean they are potentially eligible if all the other inclusion criteria are met.

4. May or may not be hospitalized
5. No symptoms or no more than 7 days of moderate symptoms at the time of screening.

Moderate symptoms may include:

- a. Moderate rhinorrhea

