**Table: Schedule of Events**

Study period	Screen	Baseline	Infusion	Follow up						
Day	-1 to 0	0	0	1	3±2	7±1	14±3	28±7	60±7	90±7
Eligibility										
Informed consent	x									
Demographic and Medical history	x									
COVID-19 symptom screen	x		x							
SARS-CoV-2 ID NOW and RT-PCR obtained for eligibility	x 									
Pregnancy test 	x									
ABO 	x									
Study Drug Administration										
Randomization		x								
Drug infusion			x							
Study Procedures										
COVID-19 Symptom screen	x		x	x	x	x	x	x	x	
Other symptoms screen	x		x	x	x	x	x	x	x	
Concomitant medications	x		x	x	x	x	x			
Vital signs	x		x 		x	x	x			
Targeted physical examination	x		x			x	x			

 A repeat ID NOW and PCR at screening is required for all participants. However, for participants with documented evidence of infection by nasal swab PCR that is positive for SARS-CoV-2 in the prior week, a positive swab is not required to enroll the participant since they were already positive in the past week and will be tested by PCR during the Infusion Visit. At screening, two swabs will be collected from each participant, one for ID NOW (or comparable rapid antigen test) and one for a PCR-based test. If ID NOW is positive, it will not be necessary to wait for the PCR based test result to confirm the positive. If the ID NOW is negative, it will be necessary to wait for the PCR test result: PCR negative will mean individual is not eligible and PCR positive will mean they are potentially eligible if all the other inclusion criteria are met.

 Urine pregnancy test for women of childbearing potential

 Assessment of ABO type on file; requires two tubes of blood drawn 5 minutes apart, as per NYP Blood Bank procedures

 Vital sign testing: Immediately prior to infusion, 10-20 minutes after start of infusion, at completion of infusion and 15-60 minutes after the end of the infusion

Study period	Screen	Baseline	Infusion	Follow up						
Day	-1 to 0	0	0	1	3±2	7±1	14±3	28±7	60±7	90±7
Assessment of composite outcome of disease severity 			x	x	x	x	x	x	x	
Adverse event monitoring			x	x	x	x	x	x	x	
Laboratory testing										
CBC and CMP 	x					x	x			
SARS-CoV-2 RT-PCR 	x		x		x	x	x	x		
SARS-CoV-2 antibody	x				x	x	x	x		x
Blood for future testing	x				x	x	x	x		
Viral culture 	x				x					

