### 4.2 Day -1 to 0 (Screening Visit+)

1. Informed consent (obtained before performing study related activities) and assignment of screening PTID
2. New York Presbyterian Hospital (NYPH) blood transfusion consent (this is the standard procedure for all transfusions of blood products at NYPH)
3. Verification of eligibility (inclusion/exclusion)
4. Locator form
5. Demographics (age, sex ethnicity, race)
6. Medical history (timing of exposure to COVID---19 source patient, acute and chronic medical condition, medications, allergies. Any medical condition arising after randomization and infusion of study product should be recorded as AE)
7. COVID---19 symptom screen (fevers, cough, rhinorrhea, sore throat, diarrhea, shortness of breath, ADLs)
8. Vital signs (pulse, blood pressure, weight, height, temperature, oxygen saturation)
9. Targeted physical examination
10. ID NOW COVID-19 and PCR test to confirm positivity for SARS-CoV-2
11. Laboratory Evaluation
  - SARS-CoV-2 testing (RT-PCR) from nasal swab (10% of the swabs will also be submitted for viral culture).
  - ABO Blood typing (two tubes), CBC, comprehensive metabolic panel
  - Serological testing: anti-SARS CoV-2 titers
  - Blood samples for future studies, including sample for peripheral blood mononuclear cells
  - Urine or serum pregnancy test for females of childbearing potential.

---

 At screening, two swabs will be collected from each participant, one for ID NOW (or comparable rapid antigen test) and one for a PCR-based test. If ID NOW is positive, it will not be necessary to wait for the PCR based test result to confirm the positive. If the ID NOW is negative, it will be necessary to wait for the PCR test result: PCR negative will mean individual is not eligible and PCR positive will mean they are potentially eligible if all the other inclusion criteria are met.

Results from laboratory tests obtained up to 7 days before enrollment may be used for the pregnancy test.

- Volume overload
  - Volume status will be assessed via (1) medical history: history of congestive heart failure and use of heart failure medications; and (2) physical exam: vital signs, lung exam, assessment for peripheral edema.
  - Enrollment will be deferred for patients who have active volume overload in order to avoid cardiovascular decompensation from the receipt of additional volume. Once the patient's volume status has improved, enrollment may then proceed. [note this is not an exclusion]

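### Section 1.5 screens asymptomatic people by PCR alone, but the eligibility text, the Schedule of Events and Section 4.2 let any participant qualify on a positive rapid test before PCR is known

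*Combined protocol and SAP*

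**What the plan says.** Section 1.5 splits screening by symptoms. On one side: "For asymptomatic individuals, PCR testing alone will be used for screening". On the other: "For symptomatic individuals, two swabs will be collected from each potential participant, one for ID NOW (or comparable rapid antigen test"), plus a second swab for PCR. It justifies accepting either positive result by a specificity of 99.7%, quoted for ID NOW. It also describes ID NOW as a molecular test intended for people whom a provider suspects of having COVID-19, within the first seven days of symptoms.

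The operational text makes no such split. Inclusion criterion 3 in Section 2.3.1 asks for "Evidence of infection by nasal swab ID NOW or PCR that is positive for SARS-CoV-2 at screening visit". Footnote 5 to that criterion, repeated as footnote 9 of the Schedule of Events, says "A repeat ID NOW and PCR at screening is required for all participants" and goes on: "At screening, two swabs will be collected from each participant, one for ID NOW (or comparable rapid antigen test) and one for a PCR-based test". Section 4.2 item 10 lists "ID NOW COVID-19 and PCR test to confirm positivity for SARS-CoV-2" for everyone. Its footnote 18, like footnotes 5 and 9, adds: "If ID NOW is positive, it will not be necessary to wait for the PCR based test result to confirm the positive".

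Footnotes 5 and 9, but not footnote 18, also waive the need for a positive screening swab when a positive PCR was documented in the prior week.

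**The concern.** A site cannot follow both rules for someone without symptoms. The choice decides who may be randomised. Under Section 1.5, an asymptomatic person enters on PCR. Under the eligibility text, a single positive rapid result is enough.

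Asymptomatic contacts are likely to have the lowest probability of infection before testing, so false positives would concentrate among them. An uninfected person who enters this way may receive 400-500 mL of plasma or 500 mL of albumin with no prospect of benefit, and remains in the intention-to-treat comparison that drives the go/no-go decision. Sites that read different sections would also enrol different populations.

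**Working it through.** **1. Is the affected route open?** Yes. Criterion 2a admits close contacts within 7 days of infusion and needs no earlier positive test. Criterion 5 admits people with no symptoms. Criterion 3 is then met by a positive ID NOW alone. PCR is also taken at screening and at the infusion visit, so a negative result would become known. No section says what happens when it is negative in someone who already qualified on a positive rapid test; the footnotes cover a negative PCR only after a negative ID NOW. Entrants by route 2b already report or document an earlier positive test, so the issue falls mainly on asymptomatic 2a entrants.

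**2. The plan's own power figures.** Inputs from Sections 3.1 to 3.3 and Table 2: 50 control and 100 plasma participants, one-sided 0.15, shift odds ratio 2. Simulating the tie-corrected Mann-Whitney test (40,000 runs, unstratified and with two equal strata) on the Table 2 percentages gives 73.8-74.3% for Scenario 1 (stated 74%) and about 81% for Scenario 2 (stated 80%). With exact odds-ratio-2 distributions, the unstratified results are 74.9% and 80.6%. The stated power stands.

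**3. Uninfected share among rapid-positive asymptomatic entrants.** Specificity 0.997 is from Section 1.5. Prevalence and sensitivity are not in the documents and are assumed.

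Share = (1 - spec)(1 - prev) / [(1 - spec)(1 - prev) + sens x prev]

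| Assumed prevalence | Sensitivity 60% | Sensitivity 80% |
|---|---|---|
| 5% | 0.00285/0.03285 = 8.7% | 0.00285/0.04285 = 6.7% |
| 10% | 0.0027/0.0627 = 4.3% | 0.0027/0.0827 = 3.3% |
| 20% | 0.0024/0.1224 = 2.0% | 0.0024/0.1624 = 1.5% |
| 30% | 0.0021/0.1821 = 1.2% | 0.0021/0.2421 = 0.9% |
| 50% | 0.0015/0.3015 = 0.5% | 0.0015/0.4015 = 0.4% |

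**4. From subgroup to trial.** The documents do not say how many of the 150 would enter this way. If one-third did (assumed), at 10% prevalence the whole-trial share is 3.3%/3 to 4.3%/3, or 1.1-1.4%: about two people.

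To show sensitivity, suppose uninfected entrants rate category 1 in both arms. Power from the exact odds-ratio-2 distributions is then:

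| Share of whole trial | Scenario 1 | Scenario 2 |
|---|---|---|
| 0% | 74.9% | 80.6% |
| 1% | 73.4% | 80.1% |
| 3% | 69.4% | 79.5% |
| 5% | 66.7% | 78.3% |

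Scenario 1 is more sensitive because Table 2 puts nobody in category 1 there. A whole-trial share of 5% is hard to reach: at 5% prevalence it would need 5/8.7 to 5/6.7, or about 58-75% of all participants, to be rapid-positive asymptomatic entrants.

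**5. The substitute test.** Section 1.5 and footnotes 5, 9 and 18 all allow "one for ID NOW (or comparable rapid antigen test) and one for a PCR-based test" or the same wording. Section 1.5 calls ID NOW a molecular test and gives its specificity only. No figure is given for an antigen test, yet the no-wait rule would cover it.

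**The case against.** The strongest case on the other side is that the consequence is small and the remedy a matter of preference. Much of this stands.

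- A reader might infer that the contradiction creates entry on an unconfirmed rapid test. It does not: Section 1.5 itself accepts ID NOW alone for symptomatic people. The contradiction decides only whether that extends to asymptomatic people.
- A reader might infer a large false-positive share. At the one documented specificity the share is a few percent or less unless prevalence is about 5% or lower. Section 2.3.1 expects mostly household contacts with extensive interaction, which argues for higher prevalence. Larger figures need an assumed antigen specificity; for example, 98% would give 18-23% at 10% prevalence. That is hypothetical.
- A reader might infer that a false positive must end in category 1 whatever the treatment. A recently exposed, high-risk person may be infected later, and categories 4 to 7 do not require a positive PCR. The power illustration is therefore a simplification.
- A reader might infer that Section 1.5 is the intended rule. The operational passages agree with one another against it, and the documents do not show which was meant.

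None of this removes the conflict, or supplies a basis for using the rapid test outside the intended use that the protocol describes.

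**Conclusion.** The point holds as an inconsistency in current, operative text about who qualifies for randomisation. Its worst documented consequence is that an asymptomatic close contact with no prior positive test can be randomised and infused on one rapid result.

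The size is modest: at 99.7% specificity and assumed sensitivity of 60-80%, about 7-9%, 3-4% or 1.5-2% of that subgroup at assumed prevalences of 5%, 10% or 20%, and under about 1.3% at 30% or more. The effect on the whole trial is smaller and cannot be fixed without the case mix. The stated power figures are not in error. The case for change rests on needless exposure of uninfected people and on sites applying different entry rules, more than on lost power.

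**What to change.** Reconcile Section 1.5, inclusion criterion 3, footnotes 5, 9 and 18, the Schedule of Events eligibility-test row and Section 4.2 item 10 to one rule for people asymptomatic at screening.

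- Aligning to Section 1.5 is the option that fits the protocol's description of ID NOW: a positive PCR before randomisation for anyone asymptomatic, with the no-wait rule limited to symptomatic people.
- State whether the waiver for a documented positive PCR in the prior week remains, and make footnote 18 agree.
- In all four places, Section 1.5 included, remove the antigen substitute from the no-wait rule or limit that rule to ID NOW. Widening it to rapid molecular tests in general would repeat the problem, because 99.7% is quoted for ID NOW and not for a class.
- Whichever rule is kept, say how a negative screening PCR is handled in someone who entered on a positive rapid test.

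The cost is wording in these places. In practice, asymptomatic participants would wait for PCR, as ID NOW-negative participants already do.
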